### For calculation regarding antibody levels/titers,

values reported as below the lower limit of quantification (LLOQ) will be replaced by 0.5 × LLOQ.

values reported as above the upper limit of quantification (ULOQ) will be converted to the ULOQ,

Missing results will not be imputed.

**Treatment arm** will be presented according to the analysis set of interest, unless otherwise specified. All the statistical analyses will be performed and presented for Cohort A and Cohort B separately. The following treatment arm labels will be used for summary purposes for Cohort A and for Cohort B tables and figures outputs, respectively:

#### **Cohort A Substudy (≥65 Years)**

mRNA 1083 40 µg + Placebo

Fluzone HD + Spikevax

Overall (All treatment arms combined; details are available below)

#### Cohort B Substudy (≥50 to <65 Years)

mRNA 1083 40 μg + Placebo

Fluarix + Spikevax

Overall (All treatment arms combined; details are available below)

The "Overall" combined group will be presented for the summaries of disposition, major protocol deviation, medical history, concomitant medication and baseline demographic only.

**Table layouts**: Tables and figures will be outputted for all the participants. Where indicated in this SAP, the following subgroups, detailed in Table 4, will be used for summary purposes. Unless otherwise specified, all subgroups are based on eCRF.

**Table 4 Subgroups Definition** 

Substudies	Subgroup Variables	Categories
Cohort A (≥65 years of	Age Group	65 to <75 years ≥75 years
age)	Influenza vaccine status since Sept 2022 (only for immunogenicity analyses)	Received previous season flu vaccine Did not receive previous season flu vaccine
	Covid vaccine status since September 2022 (only for SARS-CoV-2 related immunogenicity analyses)	Received previous Covid vaccine Did not receive previous Covid vaccine
	Number of prior covid vaccines (only for SARS-CoV-2 related immunogenicity analyses)	No Dose, 1 - 2 Doses, 3 Doses, 4 Doses, >=5 Doses
	Baseline SAS-CoV-2 Infection Status (only for SARS-CoV-2 related immunogenicity analyses)	Positive, Negative
	Race	White Black or African American Asian American Indian or Alaska Native Native Hawaiian or Other Pacific Islander Other (combining Not Reported and Unknown)
	Ethnicity	Hispanic or Latino Not Hispanic or Latino
	Sex	Male Female
	BMI	$ < 30 \text{ kg/m}^2 $ $ \ge 30 \text{ kg/m}^2 $
Cohort B (50 to <65 years of age)	Influenza vaccine status since Sept 2022 (only for immunogenicity analyses)	Received previous season flu vaccine Did not receive previous season flu vaccine
	Covid vaccine status since September 2022 (only for SARS CoV 2 related immunogenicity analyses)	Received previous Covid vaccine Did not receive previous Covid vaccine

	Number of prior covid vaccines (only for SARS CoV 2 related immunogenicity analyses)	No Dose, 1 - 2 Doses, 3 Doses, 4 Doses, >=5 Doses
	Baseline SAS-CoV-2 Infection Status (only for SARS-CoV-2 related immunogenicity analyses)	Positive, Negative
	Race	White Black or African American Asian American Indian or Alaska Native Native Hawaiian or Other Pacific Islander Other (combining Not Reported and Unknown)
	Ethnicity	Hispanic or Latino Not Hispanic or Latino
	Sex	Male Female
	BMI	$ < 30 \text{ kg/m}^2 $ $ \ge 30 \text{ kg/m}^2 $

## **6.2** Background Characteristics

#### 6.2.1 Participant Disposition

The number and percentage of participants in each of the following disposition categories will be summarized by treatment arm (as defined in Section 6.1) based on the Randomization Set, Safety Set, and PP Immunogenicity Set (as defined in Section 5):

Received study injection

Completed the study

Prematurely discontinued the study and the reason for discontinuation

This study treatment consists of 2 injections administered IM, thus discontinuation from study treatment is applicable if a participant receives only 1 of the 2 planned injections. A Participant is considered to have completed the study if he or she has completed the study including the last Day 181 scheduled procedure (SoA).

Participant randomization and disposition listings will be provided, including randomization information such as randomization date, number, planned and actual treatment arm and stratification used, informed consent, participants who received study injection, participants who completed study, participants who discontinued from study, with reasons for discontinuation. In

addition, randomized participants with any inclusion and exclusion criteria deviation will also be provided in a listing.

The number of participants in the following categories will be summarized based on Participants Screened:

Number of participants screened

Number and percentage of screen failure participants and the reason for screen failure

The percentage of participants who screen failed will be based on the number of participants screened. The reason for screen failure will be based on the number of participants who screen failed.

A screen failure listing will be provided including information on the screen failed participants and the reasons for screen failure.

The number and percentage of participants randomized with respect to each combined stratification factor at randomization by IRT will be summarized by treatment arm (as defined in Section 6.1) based on the Randomization Set:

#### **Cohort A Substudy (≥65 Years)**

≥65 to <75 years and Received an influenza vaccine since September 2022,

≥65 to <75 years and Did Not Receive an influenza vaccine since September 2022,

≥75 years and Received an influenza vaccine since September 2022,

≥75 years and Did Not Receive an influenza vaccine since September 2022,

### **Cohort B Substudy (≥50 to <65 Years)**

Received an influenza vaccine since September 2022,

Did Not Receive an influenza vaccine since September 2022,

If IRT and eCRF stratum are not concordant, then a concordance table will be presented, by treatment arm (as defined in Section 6.1) based on the Randomization Set, with the number and percentage of patients in IRT randomization stratum and actual stratum derived from eCRF.

The number and percentage of participants in the following Analysis Sets (see Section 5) will be summarized by treatment arm (as defined in Section 6.1) based on the Randomization Set:

Randomization Set,

Full Analysis Set,

Immunogenicity Set,

Per Protocol Immunogenicity Set,

Per Protocol Immunogenicity Set for MN Assay,

Safety Set,

Solicited Safety Set.

For Solicited Safety Set, the percentage will be based on the number of participants in the treatment arm within the Safety Set (as treated). A summary of reasons for participants excluded from the Per Protocol Immunogenicity Set will also be provided.

A listing, including information related to the different Analysis Sets of the randomized participants as well as the reason for exclusion from analysis set will be added.

### **6.2.2** Demographics and Baseline Characteristics

Descriptive statistics will be calculated for the following continuous demographic and baseline characteristics:

Age (years)

Weight (kg)

Height (cm)

Body mass index (kg/m2)

The number and percentage of participants will be provided for the following categorical variables:

Age group ( $\geq$ 65 to <75 years old,  $\geq$ 75 years for Cohort A,  $\geq$  50 to < 65 years old for Cohort B, separately) per age reported on the eCRF

BMI group ( $< 30 \text{ kg/m2}, \ge 30 \text{ kg/m2}$ )

Sex (Male, Female)

Race (White, Black or African American, Asian, American Indian or Alaska Native, Native Hawaiian or Other Pacific Islander, Multiracial, Other, Unknown, Not Reported)

Ethnicity (Hispanic or Latino, Not Hispanic or Latino, Not Reported, Unknown)

Frailty Status for participants ≥65 years of age (Edmonton Frail Scale total score 0-3: Fit, 4-5: Vulnerable, 6 or more: Frail)

Influenza vaccine status in the most recent influenza season (received or not received since Sept 2022) per eCRF

Covid vaccine status since September 2022 (received or not received)

Number of Covid vaccinations (No Dose, 1-2 Doses, 3 Doses, 4 Doses, >=5 Doses)

Childbearing Potential for female participants (Yes/No) and reason if "No"

Baseline SARS-CoV-2 RT-PCR Results (positive, negative, or missing)

Baseline Elecsys Anti-SARS-CoV-2 Results (positive, negative, or missing)

Baseline SARS-CoV-2 Status (positive, negative, or missing)

Baseline Influenza Infectious Status (positive, negative, or missing)

The summaries will be provided separately for all analysis sets (except for Immunogenicity Set and Solicited Safety Set) defined in the Section 5, by treatment arm (as defined in Section 6.1).

Demographic and baseline characteristics will be provided listings for randomized and screened failed participants. The number and percentage of participants randomized by country and site will be provided as well.

## **6.2.3** Medical History

Medical history data will be coded by system organ class (SOC) and preferred term (PT) using the Medical Dictionary for Regulatory Activities (MedDRA).

The number and percentage of participants with any medical history will be summarized by SOC and PT based on the Safety Set, by treatment arm (as defined in Section 6.1). A participant will be counted only once for multiple events within each SOC and PT. SOC will be displayed in internationally agreed order. PT will be displayed in descending order of frequency of the "1083 + Placebo" group and then alphabetically within SOC. Medical history data will be presented in a listing.

#### 6.2.4 Prior and Concomitant Medications

Prior and concomitant medications and non-study vaccination will be coded using the World Health Organization (WHO) drug dictionary (WHODD). The summary of concomitant medications will be based on the Safety Set. Categorization of prior, concomitant, and post medications and imputation rules for missing/partial dates is summarized in Appendix D.

An overall summary with the number and percentage of participants using concomitant medications and non-study vaccination that continued or newly received at or after the injection, during the 7-day follow-up period (i.e., on the day of injection and the 6 subsequent days) and during the 28 day follow-up period after the injection (i.e., on the day of injection and the 27 subsequent days) will be provided by treatment arm (as defined in Section 6.1) as follows:

Any concomitant medications and non-study vaccination within 7 days postinjection Any concomitant medications and non-study vaccination within 28 days postinjection Any seasonal influenza or COVID-19 Vaccine within 28 days postinjection

An additional summary table of concomitant medications and non-study vaccination that continued or newly received at or after the injection through 28 days will be provided by PT in descending frequency based on "1083 + Placebo" group.

Medications taken to prevent or treat pain or fever will be collected in the electronic diary (eDiary). A summary table will be provided based on the Solicited Safety Set by treatment arm (as defined in Section 6.1), including within 7 days after injection.

Prior and concomitant medications and non-study vaccination will be presented in a listing. Medications taken to prevent or treat pain or fever will be presented as well (see Section 6.5.1.1 on solicited ARs listings).

Concomitant Procedures will be presented in a listing.

#### **6.2.5** Protocol Deviations

The noncompliance may be either on the part of the participant, the Investigator, or the study site staff (or delegate). As a result of deviations, corrective actions are to be developed by the site

and implemented promptly. Major protocol deviations are a subset of protocol deviations that may affects primary efficacy and safety assessments (as applicable), the safety or mental integrity of a subject, or the scientific value of the trial project. Major protocol deviations rules will be developed and finalized before database lock.

The number and percentage of the participants with each major protocol deviation type will be provided by treatment arm (as defined in Section 6.1), based on the Randomization Set.

Selected major protocol deviations might impact critical or key study data such as the immune response. Participants with such deviations will be excluded from the PPIS and PPIS for MN assay. Such major protocol deviations will be determined and documented by Sponsor prior to database lock and unblinding. Reasons of exclusion from the PPIS set will be summarized. Major protocol deviations will be presented in a listing.

#### 6.2.6 Study Exposure

Study duration (the study duration calculation is available in Section 6.1) will be summarized by treatment arm (as defined in Section 6.1) since randomization, and since the study injection based on Safety Set. Study vaccine administration data will be presented in a listing. Participants with any dosing errors will also be presented in a separate listing.

### **6.2.7 COVID-19 Impact**

A listing will be provided for COVID-19 impact on missed or out of window visits or assessments for participants in Safety Set.

## 6.3 Immunogenicity Analyses

The primary analysis population for immunogenicity will be the Per Protocol Immunogenicity Set, unless otherwise specified. A subset of participants will be randomly selected from the FAS of cohort A and B, respectively, to be tested by MN assay for the secondary objective. The sampling method and process to obtain the subset are described in Appendix I. The analysis population for this immunogenicity subset will be the Per Protocol Immunogenicity Set for MN Assay, unless otherwise specified. Some of the further immunogenicity analyses may be performed in a subset of participants.

For humoral immunogenicity (except for MN assay) on Day 1 and Day 29, samples will be collected and analyzed for all participants of each cohort. For Day 181, samples will be collected and analyzed for the first 800 participants of each cohort. Plasma and serum from humoral immunogenicity samples will be stored for potential future use.

The following analytes will be measured:

Influenza: Serum antibody level as measured by HAI assay and serum nAb level as measured by microneutralization assay.

SARS-CoV-2: Serum nAb levels as measured by PsVNA assay by enzyme linked immunosorbent assay or multiplex assay specific to the SARS-CoV-2 proteins.

Please refer to Appendix C for details regarding the analysis visit window or in case of multiple postbaseline assessment available.

For the primary, secondary, and exploratory endpoints, the GM level (GMT) will be calculated using the following formula (Nauta, 2011):

$$2^{\left\{\frac{\sum_{i=1}^{n} log_2(t_i)}{n}\right\}}$$

where  $t_1, t_2, ..., t_n$  are *n* observed immunogenicity titers or levels.

The 95% CIs for GM level will be calculated based on the t distribution of the log-transformed values then back transformed to the original scale for presentation, unless otherwise specified.

# 6.3.1 Primary Immunogenicity Endpoints Analysis

For each substudy, there is a total of five co-primary endpoints based on GM level, and five co-primary endpoints based on seroconversion and seroresponse for the vaccine-matched strains. The primary objective of this study is to use the immunogenicity response to infer efficacy in participants receiving mRNA-1083.

#### 6.3.1.1 Cohort A Substudy (≥65 Years): Primary Analyses

The primary objective of Cohort A is to evaluate the immunogenicity response between the participants receiving mRNA-1083 (40  $\mu$ g) + Placebo and those receiving Fluzone HD + Spikevax among the adults  $\geq$ 65 years of age. Immune responses for influenza, as measured by GM level and SCR at Day 29 by HAI assay in the group of mRNA-1083 (40  $\mu$ g) + Placebo, will be compared with those in the participants receiving Fluzone HD + Spikevax for all 4 influenza strains. Immune responses for SARS-CoV-2, as measured by GM level and SRR at Day 29 by PsVNA in the group of mRNA-1083 (40  $\mu$ g) + Placebo, will be compared with those participants receiving Fluzone HD + Spikevax for the matched strain.

#### Five Co-primary Endpoints Based on Influenza and SARS-CoV-2 GM level at Day 29

An ANCOVA model will be carried out including the log-transformed HAI or PsVNA levels at Day 29 as the dependent variable, the treatment group as the fixed variable and log transformed baseline HAI or PsVNA levels as a fixed covariate. The model will be adjusted for the stratification factors (age group: 65 to <75 years of age and 75 years of age or greater and the influenza vaccine status in the most recent influenza season: received or not received since September 2022).

The GM level will be estimated by the geometric least square mean (GLSM) from the ANCOVA model for each treatment arm and corresponding 2-sided 95% CI will be provided. The GLSM and its corresponding CI in log-transformed scale will be back-transformed to the original scale to obtain an estimate of the GM level.

GMR will be estimated by the ratio of GLSM and the corresponding 2-sided 95% and 97.5% CI to assess the immune response difference between the group of mRNA-1083 (40  $\mu$ g) + Placebo and Fluzone HD + Spikevax and presented by treatment arm (as defined in Section 6.1).

For each strain of influenza and SARS-CoV-2, the NI of GM level will be considered demonstrated between the group of mRNA-1083 (40  $\mu$ g) + Placebo and Fluzone HD + Spikevax if the lower bound of the 97.5% CI of the GMR is >0.667 based on the prespecified NIM of 1.5.

GM level and GMR at Day 29 will be plotted.

# Five Co-primary Endpoints Based on Influenza SCR and SARS-CoV-2 SRR at Day 29

Seroconversion and seroresponse are defined as follow:

**Influenza**: Percentage of participants with seroconversion, defined as a Day 29 post-injection level  $\geq$ 1:40 if Baseline is  $\leq$ 1:10 or a 4-fold or greater rise if Baseline is  $\geq$ 1:10 in anti-HA antibodies measured by HAI assay.

**SARS-CoV-2**: Percentage of participants with seroresponse, defined as a Day 29 post-injection level  $\geq$ 4-fold rise if Baseline is  $\geq$  LLOQ or  $\geq$ 4×LLOQ if Baseline value is <LLOQ in the nAb values measured by PsVNA.

The number and percentage of participants with either seroconversion (for influenza) or seroresponse (for SARS-CoV-2) postvaccination at Day 29 will be provided along with the two-sided 95% CI of SCR or SRR estimated using the Clopper-Pearson method and presented by treatment arm (as defined in Section 6.1). The difference in either SCR or SRR between the group of mRNA-1083 (40  $\mu$ g) + Placebo and Fluzone HD + Spikevax, along with its 95% and 97.5% CI estimated using the Miettinen-Nurminen's method will be provided to assess the immune response difference.

For each strain of influenza and SARS-CoV-2, the NI of SCR or SRR will be considered demonstrated between the group of mRNA-1083 (40  $\mu$ g) + Placebo and Fluzone HD + Spikevax if the lower bound of the 97.5% CI of the SCR or SRR difference is >-10% based on the prespecified NIM of 10%.

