6.3. Assignment to Study Intervention

Randomization will be performed using an IRT.

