For influenza, the SCR at Day 29 is defined as the proportion of participants with either a preinjection HAI level $\leq 1:10$ and a postinjection HAI level $\geq 1:40$, or a preinjection HAI level $\geq 1:10$ and a minimum 4-fold rise in postinjection HAI antibody level. The SCR difference Day 29 is defined as the difference between the SCR at Day 29 among those participants receiving mRNA-1083 ($40~\mu g$) + Placebo and the SCR at Day 29 among those participants receiving Fluzone HD + Spikevax.

For SARS-CoV-2, the SRR at Day 29 is defined as the proportion of participants with either GMFR in nAb levels of \geq 4-fold postinjection compared with Day 1 in those with Baseline level \geq LLOQ, or postinjection level \geq 4×LLOQ if Baseline level is <LLOQ. The SRR difference at Day 29 is defined as the difference between the SRR at Day 29 among those participants receiving mRNA-1083 (40 μ g) + Placebo and the SRR at Day 29 among those participants receiving Fluzone HD + Spikevax.

The success criteria of non-inferiority for GM level are met if H^{1}_{0} is rejected at two-sided 0.025 level on the 5 coprimary endpoints for GM level. Similarly, the success criteria for SCR or SRR are met if H^{2}_{0} is rejected at two-sided 0.025 level on the 5 coprimary endpoints for SCR or SRR.

Secondary Endpoints

If the noninferiority success criteria of the coprimary endpoints for GM level are met, the following hypotheses will be tested sequentially to support secondary objectives (See Figure 2):

The null hypothesis H^3_0 : for each of the 4 influenza strains (2 A strains: H1N1, H3N2 and 2 B strains: Victoria, Yamagata), the immunogenicity response to mRNA-1083 (40 µg) + Placebo, as measured by GM level at Day 29 using HAI assay for influenza, is not superior to that in participants who received Fluzone HD + Spikevax. The superiority in GM level in participants who received mRNA-1083 (40 µg) + Placebo compared to that of participants who received active comparator will be demonstrated by the lower bound of the (100%- α_1) CI of the GMR ruling out 1 (lower bound >1) for all 4 influenza strains. It will be tested at a two-sided α_1 =5% level if noninferiority is demonstrated for GM level (H^1_0 rejected) and SCR or SRR (H^2_0 rejected); and at a two-sided α_1 =2.5% level if non-inferiority is only demonstrated for GM level (H^1_0 rejected).

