For SARS-CoV-2, the SRR at Day 29 is defined as the proportion of participants with either a GMFR in nAb levels of \geq 4-fold postinjection compared with Day 1 in those with Baseline level \geq LLOQ or postinjection level \geq 4×LLOQ if Baseline level is <LLOQ. The SRR difference at Day 29 is defined as the difference between the SRR at Day 29 among those participants receiving mRNA-1083 (40 μ g) + Placebo and the SRR at Day 29 among those receiving Fluarix + Spikevax.

The success criteria of non-inferiority for GM level are met if H^1_0 is rejected at two-sided 0.025 level on the 5 coprimary endpoints for GM level. Similarly, the success criteria for SCR or SRR are met if H^2_0 is rejected at two-sided 0.025 level on the 5 coprimary endpoints for SCR or SRR.

Secondary Endpoints

If the noninferiority success criteria of the coprimary endpoints for GM level are met, the following hypotheses will be tested sequentially to support secondary objectives (See Figure 2):

The null hypothesis H^3_0 : for each of the 4 influenza strains (2 A strains: H1N1, H3N2 and 2 B strains: Victoria, Yamagata), the immunogenicity response to mRNA-1083 (40 µg) + Placebo, as measured by GM level at Day 29 using HAI assay for influenza, is not superior to that in participants who received Fluarix + Spikevax. The superiority in GM level in participants who received mRNA-1083 (40 µg) + Placebo compared to that of participants who received active comparator will be demonstrated by the lower bound of the (100%- α_1) CI of the GMR ruling out 1 (lower bound >1) for all 4 influenza strains. It will be tested at a two-sided α_1 =5% level if noninferiority is demonstrated for GM level (H^1_0 rejected) and SCR or SRR (H^2_0 rejected); and at a two-sided α_1 =2.5% level if non-inferiority is only demonstrated for GM level (H^1_0 rejected).

If the superiority success criteria for GM levels at Day 29 using HAI assay for influenza are met $(H^3_0 \text{ rejected})$, the null hypothesis $H^4_0 \text{ will}$ be tested: for the SARS-CoV-2 strain (Omicron XBB.1.5), the immunogenicity response to mRNA-1083 (40 μ g) + Placebo, as measured by GM level at Day 29 using PsVNA is not superior to that in participants who received Fluarix + Spikevax. The superiority in GM level in participants who received

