#### 4.4 Randomization

Randomization will be performed using an interactive response technology (IRT) by a 3rd party vendor.

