#### **Cohort A Substudy (≥65 Years)**

In Cohort A randomization (in a 1:1 ratio) will be stratified by age groups (65 to <75 years and  $\geq$ 75 years of age where at least 10% of participants are  $\geq$ 75 years of age) and the influenza vaccine status in the most recent influenza season (received or not received since September 2022).

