### **Cohort B Substudy (≥50 to <65 Years)**

In Cohort B randomization (in a 1:1 ratio) will be stratified by the influenza vaccine status in the most recent influenza season (received or not received since September 2022).

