**Influenza**: Percentage of participants with seroconversion, defined as a Day 29 post-injection level  $\geq$ 1:40 if Baseline is  $\leq$ 1:10 or a 4-fold or greater rise if Baseline is  $\geq$ 1:10 in anti-HA antibodies measured by HAI assay.

**SARS-CoV-2**: Percentage of participants with seroresponse, defined as a Day 29 post-injection level  $\geq$ 4-fold rise if Baseline is  $\geq$  LLOQ or  $\geq$ 4×LLOQ if Baseline value is  $\leq$ LLOQ in the nAb values measured by PsVNA.

The number and percentage of participants with either seroconversion (for influenza) or seroresponse (for SARS-CoV-2) postvaccination at Day 29 will be provided along with the two-sided 95% CI SCR or SRR estimated using the Clopper-Pearson method and presented by treatment arm (as defined in Section 6.1). The difference in either SCR or SRR between the group of mRNA-1083 (40  $\mu$ g) + Placebo and Fluarix + Spikevax, along with its 95% and 97.5% CI estimated using the Miettinen-Nurminen's method will be provided to assess the immune response difference.

For each strain of influenza and SARS-CoV-2, the NI of SCR or SRR will be considered demonstrated between the group of mRNA-1083 (40 µg) + Placebo and Fluarix + Spikevax if the

lower bound of the 97.5% CI of the SCR or SRR difference is >-10% based on the prespecified NIM of 10%.

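### The SCR/SRR difference is analysed without the randomisation strata: valid, but it gives up a little precision that a stratified Miettinen-Nurminen interval would keep (minor)

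*SAP*

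**What the plan says.** - **Interval method.** SAP 6.3.1.1 (Cohort A) presents the SCR or SRR difference "along with its 95% and 97.5% CI estimated using the Miettinen-Nurminen's method will be provided to assess the immune response difference". SAP 6.3.1.3 (Cohort B) and Protocol 9.5.1 (both cohorts) name the same method. None of them mentions strata, weights or covariates.
- **Estimand.** Protocol 9.2 and SAP 4.2.1.1 and 4.2.2.1 define a plain difference of overall arm rates: "The SCR difference Day 29 is defined as the difference between the SCR at Day 29 among those participants receiving" the one regimen and the same rate in the other. The SRR definition has the same form: "The SRR difference at Day 29 is defined as the difference between the SRR at Day 29 among those participants receiving".
- **Use.** H2 needs the 97.5% lower bound above -10 points on all five endpoints. H5 needs the 95% lower bound above 0 on all four influenza strains, and H6 the same for SRR. The sections that set H5 and H6 name no interval method; the link runs through the 95% interval in SAP 6.3.1.
- **Design.** SAP 4.4: "In Cohort A randomization (in a 1:1 ratio) will be stratified by age groups" and by influenza vaccine status; "In Cohort B randomization (in a 1:1 ratio) will be stratified by the influenza vaccine status in the most recent influenza season". Blocking is not stated; Protocol 6.3 says only "Randomization will be performed using an IRT".
- **The other co-primary family.** The ANCOVA for the GMR adjusts for these stratification factors and for baseline titre.
- **Nearest related text.** SAP 6.3.1.2 and 6.3.1.4 mention adjustment for the stratification factors where applicable, but only for subgroup analyses, and name no stratified method for a rate difference.

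**The concern.** The two co-primary families treat the same design differently, and no reason is given. When strata predict the outcome and arms are balanced within them, the crude interval counts between-stratum variation as noise although the design has removed it. The interval is then wider than the data require and the test slightly conservative. If allocation is not blocked, the crude test has its nominal error, but stratifying still gains power.

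The interval decides more than H2. H2 also determines whether H3 and H4 are tested at 5% or 2.5%, and whether H5 can be tested at all. Both H2 and H5 require every endpoint to pass, so small losses per endpoint accumulate. No loss is claimed for SRR or H6, because there is no stated reason to expect these strata to predict the SARS-CoV-2 response.

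**Working it through.** **Inputs from the documents (SAP 4.3.1).** 2000 randomised per arm with 15% drop-out, so 2000 × 0.85 = 1700 evaluable. Rates are 68 vs 70% (two A strains, SARS-CoV-2) and 58 vs 60% (two B strains). The margin is 10 points at two-sided 0.025, so z = 2.241.

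**Assumptions (no figures in the documents).** A share w = 65% previously vaccinated; response rates lower in the vaccinated stratum by g = 10, 20 or 30 points; the same treatment difference in both strata.

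**1. The plan's own power.** Per endpoint, power = Φ((d + 0.10)/SE − 2.241).
- 68 vs 70%: SE = √((0.68×0.32 + 0.70×0.30)/1700) = 0.01586; power 99.75%.
- 58 vs 60%: SE = 0.01687; power 99.38%.
- Joint, independent: 0.9975³ × 0.9938² = 98.0%. The stated floor of 95% is met.

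**2. Width.** Stratum rates are p − (1−w)g and p + wg. The within-stratum variance per arm is p(1−p) − w(1−w)g². At g = 0.30, w(1−w)g² = 0.65×0.35×0.09 = 0.0205, so for 68 vs 70% SE_within = √((0.4276 − 0.0410)/1700) = 0.01508.

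| Gap (points) | Excess width of unstratified CI | Same, w from 50 to 80% | 97.5% lower bound, 68 vs 70% |
|---|---|---|---|
| 0 | 0 | 0 | -5.55% (both) |
| 10 | about 0.5% | 0.3–0.6% | -5.54% stratified |
| 20 | about 2% | 1.4–2.4% | -5.48% stratified |
| 30 | about 5% | 3.1–5.7% | -5.38% stratified |

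**3. H2 power.** Unstratified power per endpoint = Φ(((d + 0.10) − 2.241·SE_pooled)/SE_true), where SE_true = SE_within if arms are balanced within strata and SE_pooled if allocation is not blocked. Stratified power = Φ((d + 0.10)/SE_within − 2.241). Multiply over five endpoints, with the gap on the four influenza strains only. Gains in percentage points for gaps of 10 / 20 / 30:

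| True difference | Balanced, independent | Balanced, correlation 0.5 (assumed) | Not blocked, independent |
|---|---|---|---|
| -2 (planned) | 0.05 / 0.2 / 0.3 | 0.04 / 0.2 / 0.3 | 0.1 / 0.4 / 0.9 |
| -3 | 0.2 / 0.8 / 1.5 | 0.2 / 0.6 / 1.2 | 0.4 / 1.5 / 3.2 |
| -4 | 0.5 / 1.9 / 4.1 | 0.3 / 1.3 / 2.8 | 0.8 / 3.1 / 6.8 |

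For example, at -4 with a 30-point gap and balanced arms, power is 69.6% unstratified and 73.6% stratified. With blocks and 15% random drop-out, about 15% of the between-stratum variance returns, so the gains at -4 become 0.5 / 2.1 / 4.5. If the gap applied to all five endpoints, the planned-case gain would be 0.1 / 0.2 / 0.4 balanced and 0.1 / 0.5 / 1.0 not blocked.

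**4. H5.** Margin 0, z = 1.960, four influenza strains, assumed true difference +5 points, balanced: gain 0.6 / 2.2 / 5.0 points (independent) or 0.4 / 1.6 / 3.6 (correlation 0.5).

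**5. Type I error.** Simulated trials with actual Miettinen-Nurminen score tests at the -10 point margin, one endpoint at 70%, nominal one-sided 1.25%, Monte Carlo SE 0.035%, gaps 10 / 20 / 30:
- Balanced: 1.27 / 1.14 / 1.00% unstratified; 1.32 / 1.26 / 1.32% stratified.
- Not blocked: 1.28 / 1.24 / 1.26% unstratified; 1.29 / 1.27 / 1.28% stratified.

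Simulated H2 power at -4, balanced, agrees with step 3: 68.5 vs 70.2% (gap 20) and 70.2 vs 74.4% (gap 30).

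**The case against.** The strongest reply is that this is a preference, not a defect. The interval is valid, the power claim is met, and at the planned -2 points stratifying moves the lower bound by at most 0.17 points when it already clears the margin by 4.45. The larger gains need gaps and true differences that the documents do not give. The not-blocked figures model an allocation that would make stratification pointless. H5 is reached only after H1 to H4 are rejected, so its gains are conditional. The crude difference also matches the displayed arm rates, and seroconversion already uses baseline through the fold-rise rule. A protocol amendment is a real cost for so little.

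Most of this stands, and it limits the point to minor. The balanced columns are the more realistic ones, and the H5 gain should be read as conditional on reaching that test. What remains is that the trial stratifies by factors it already records and adjusts for them in one co-primary family. Using them in the other needs no new data and does not raise type I error. The fold-rise rule does not remove a stratum effect: response rates can still differ by prior vaccination. The documents never call the interval unstratified; that is inferred from their silence and from the crude definitions.

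**Conclusion.** The point holds as a minor matter of analysis choice. As written, the SCR/SRR interval ignores the randomisation strata. It is valid, and H2 power at the planned rates is about 98.0%. The precision given up is nil if the strata do not predict seroconversion, and about 0.5 to 5% of interval width for gaps of 10 to 30 points at 65% vaccinated. The gain in H2 power from stratifying is 1 point or less at the planned difference. It is noticeable only if the truth is worse: 0.5 to 4.1 points at -4 with balanced arms and independent endpoints, and less with correlated endpoints. A modest superiority effect is the other case where it shows, for H5. These sizes rest on assumed stratum gaps and vaccinated share, and they model vaccine status alone, not the age strata of Cohort A.

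**What to change.** Before unblinding, amend Protocol 9.5.1 and SAP 6.3.1.1 and 6.3.1.3:

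- Make the stratified Miettinen-Nurminen interval primary for the SCR and SRR differences, at both 95% and 97.5%.
- Strata: age group by influenza vaccine status in Cohort A; influenza vaccine status in Cohort B.
- Weights: Mantel-Haenszel, n1·n2/(n1+n2) per stratum.
- Source: strata as randomised in IRT, as SAP Appendix I does for sampling, with eCRF-derived strata as a sensitivity analysis if the two disagree (SAP 6.2.1 already plans a concordance table).
- Keep the unstratified interval as supportive.
- In Protocol 9.2 and SAP 4.2.1.1 and 4.2.2.1, redefine the difference as the weighted average of within-stratum differences.

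**Cost.** Protocol 9 requires an amendment when the method for a primary hypothesis changes, with the approvals in Protocol 10.1.1. The programming is a standard software option and the power section needs no change. The smallest Cohort A stratum (75 or older, not vaccinated) would hold about 80 to 200 of 4000 participants if 10% are 75 or older and 20 to 50% of those are unvaccinated (assumed: 400 × 0.20 to 400 × 0.50). That is enough for a stratified score interval.

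If the sponsor finds an amendment disproportionate, the SAP should at least say that the interval is unstratified and prespecify the stratified one as a sensitivity analysis.
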